6.2.4 Dose determining for tablet formulation

A relative bioavailability study in HVs, CINC280X2103 study, was conducted to compare the relative bioavailability of INC280 tablet to INC280 capsule. The results of this study showed that following a single oral administration of 600 mg INC280 in healthy subjects, both formulations had similar Tmax; tablets however provided higher systemic exposures (Cmax and AUC) and lower inter-subject variability. The exposure geometric mean ratios (tablet vs. capsule) were around 2 to 3. As of 3-Nov-2014, preliminary tablet PK data are available from 16 patients of tablet cohorts at different doses in various INC280 studies (i.e., 200 and 400 mg bid single agent in CINC280X1101 study, 200 mg bid in combination with gefitinib in CINC280X2202 study, and 400 mg bid single agent in CINC280X2102 study). INC280 tablet showed generally lower inter-subject variability than capsule (CV% typically $<50\%$ for tablet, whereas $>50\%$ for capsule). Based on the limited data, mean AUC and Cmax at steady-state following administration of INC280 tablets at 400 mg bid was higher than that following capsules at 600 mg bid (RP2D in CINC280X2102 study), but in the range considering the CV%. Based on the tablet PK and safety data from these studies, the dosage of INC280 at 400 mg bid in tablet has been declared as RP2D in CINC280X2102 study, and is further evaluated in CINC280X1101 study and CINC280X2202 study. Therefore, 400 mg bid is determined to be the dose of tablet formulation in the dose expansion part of this study. When the INC280 tablet formulation is available, patients who are newly enrolled may start at INC280 400 mg bid tablet treatment. Patients who have been treated with INC280 600 mg bid capsules, in compliance with the local regulation, may switch at the beginning of the next scheduled visit with INC280 400 mg bid tablet treatment.

6.2.5 Dose modification and delay

For patients who do not tolerate the protocol-specified dosing scheme, dose adjustments and interruptions are permitted. All dose modifications should be based on the worst preceding toxicity (CTCAE version 4.03). Once a dose reduction has occurred, the dose level may not be re-escalated during subsequent treatment cycles with INC280. In addition, in the Dose Determining Part, a patient must discontinue treatment with INC280 if, after treatment is resumed at a lower dose, the toxicity recurs with the same or worse severity. In the Dose Expansion Part, a patient must discontinue treatment with INC280 if, after treatment is resumed at the lowest allowed dose (200 mg BID, tablet), the toxicity recurs with the same or worse severity. All interruptions or modifications to study drug administration must be recorded on the Dose Administration Record eCRF.

If a dose delay of >21 days is required, then the investigational treatment with INC280 must be discontinued. [Table 6-3](#), [Table 6-4](#), [Table 6-5](#), [Table 6-7](#) and [Table 6-8](#) provide the guidelines to be followed for dose modification of the study drug in the event of toxicities. Included are

also instructions for re-initiation of study treatment once sufficient recovery of toxicity is seen. **Any dosing modifications that are not in accordance with the guidelines in Table 6-3, Table 6-4, Table 6-5, Table 6-7 and Table 6-8 (Andrew et al 2010) must be discussed with Novartis.** Any dose change to the study drug must be recorded on the eCRF. The study visit schedule should be followed irrespective of any study drug interruption.

In exceptional situations, study treatment may continue even if there is a dose interruption of >21 days or the patient experienced disease progression. The decision to allow for continuation of treatment will be made on a case-by-case basis following discussion between Novartis and the investigator. Situations that may allow for continuation of treatment include the following:

- A dose delay of >21 days has occurred but the patient is clearly benefiting from study treatment (i.e., SD, PR, or CR) and it is the investigator's opinion that no safety concerns are present.
- A patient with disease progression may be allowed to continue study treatment if it is in the best interest of the patient to continue treatment. Examples of situations that may allow for continuation of therapy include cystic lesions, mixed responses, and new brain metastases that are treatable with stereotactic radiotherapy or surgery.

Table 6-3 and **Table 6-4** describe respectively for the Dose-Determining Part and Dose Expansion Part, the starting dose and the study drug dose modification to be followed in case of study drug related toxicities. For each patient in Dose Expansion Part treated with INC280 tablets, a maximum of 2 dose level modifications is allowed after which the patient must be discontinued from treatment. The lowest dose allowed, 200 mg BID in tablets is expected to be pharmacologically active, as the observed steady state plasma trough concentrations ([CINC280X1101], [CINC280X2202], n=6) were above the concentration associated with full cMET inhibition in xenograft mice models (EC90, 120 nM total concentration).

Table 6-3 Dose-Determining Part study drug dose reductions

Dose level	Dose and schedule (capsule)	Increment from previous dose
-1	200 mg bid	-33% of starting dose
0	300 mg bid	Starting dose for Dose-Determining Part

Table 6-4 Dose Expansion Part study drug dose reductions

Dose level	Dose and schedule (capsule)	Increment from previous dose
-1	450 mg bid (capsule)	-25% of starting dose
0	600 mg bid (capsule)	Starting dose for Expansion Part

Dose level	Dose and schedule (tablet)	Increment from previous dose
-2	200mg bid (tablet)	-50% of starting dose
-1	300 mg bid (tablet)	-25% of starting dose
0	400 mg bid (tablet)	Starting dose for Expansion Part

Table 6-5 Recommended dosing guidelines for study drug-related toxicities

Recommended dose modifications of INC280	
Worst toxicity CTCAE v4.03 grade	Recommended dose modifications any time during a cycle of therapy, including intended day of dosing
Hematologic	
ANC decreased (Neutropenia) Grade 1 (LLN - 1500/mm ³ or LLN – 1.5x10 ⁹ /L) Grade 2 (< 1500 - 1000/mm ³ or <1.5 – 1.0x10 ⁹ /L) Grade 3 (< 1000 - 500/mm ³ or < 1.0 – 0.5x10 ⁹ /L) Grade 4 (< 500/mm ³ or < 0.5x10 ⁹ /L)	Maintain dose level Maintain dose level Discontinue dose until resolved to ≤ grade 1 or baseline, then: If resolved in ≤ 7 days, then maintain dose level If resolved in > 7 days, then ↓ 1 dose level Discontinue dose and patient from study treatment.
Febrile neutropenia ANC < 1.0 x 10 ⁹ /L or 1000/mm ³ and a single temperature of >38.3°C (101 °F) or a sustained temperature of >=38 °C (100.4 ° F) for more than one hour.	Discontinue dose until resolved, then: If resolved in ≤ 7 days, then resume treatment at ↓ 1 dose level. If resolved in > 7 days, then discontinue dose and patient from study treatment
Platelet count decreased (Thrombocytopenia) Grade 1 or 2 (< LLN – 50x10 ⁹ /L) Grade 3 (<50 – 25x10 ⁹ /L) Grade 4 (<25x10 ⁹ /L)	Maintain dose level Discontinue dose until resolved to ≤ grade 1 or baseline, then: If resolved in ≤7 days, then maintain dose level If resolved in > 7 days, then ↓ 1 dose level Discontinue dose until resolved to ≤ grade 1 or baseline, then ↓ 1 dose level
Renal	
Serum creatinine Grade 1 (> ULN – 1.5 x ULN) Grade 2 (> 1.5 - 3.0 x ULN) Grade 3 or 4 (> 3.0 x ULN)	Maintain dose level Discontinue dose until resolved to ≤ grade 1 or baseline, then maintain dose level. Patients will be instructed to increase their fluid intake until resolution to ≤ grade 1 or baseline. Discontinue dose until resolved to ≤ grade 1 or baseline, then resume treatment at ↓ 1 dose level. Patients will be instructed to increase their fluid intake until resolution to ≤ grade 1 or baseline. If grade 4 event recurs at any point during participation, discontinue study treatment.

Recommended dose modifications of INC280	
Worst toxicity CTCAE v4.03 grade	Recommended dose modifications any time during a cycle of therapy, including intended day of dosing
Hepatic	
Isolated Total Bilirubin ^a	
Grade 1 (> ULN – 1.5 x ULN)	Maintain dose level with liver function tests (LFTs)* monitored
Grade 2 (>1.5 - 3.0 x ULN)	Omit/delay dose until resolved to ≤ grade 1 or baseline, then: If resolved in ≤ 7 days, maintain dose level If resolved in > 7 days, ↓ 1 dose level
Grade 3 (> 3.0 - 10.0 x ULN)	Omit/delay dose until resolved to ≤ grade 1 or baseline, then: If resolved in ≤ 7 days, ↓ 1 dose level If resolved in > 7 days, discontinue patient from study treatment
Grade 4 (> 10.0 x ULN)	Discontinue dose and patient from study treatment.
Isolated AST or ALT	
Grade 1 or 2 (> ULN - 5.0 x ULN)	Maintain dose level with liver function tests (LFTs)* monitored
Grade 3 (> 5.0 – 20.0 x ULN)	Omit/delay until resolved to ≤ grade 1 or ≤ grade 2 if grade 2 elevation at baseline, then: If resolved in ≤ 7 days, maintain dose level of INC280 If resolved in > 7 days, ↓ 1 dose level of INC280 Discontinue dose and patient from study treatment.
Grade 4 (>20.0 x ULN)	

Recommended dose modifications of INC280	
Worst toxicity CTCAE v4.03 grade	Recommended dose modifications any time during a cycle of therapy, including intended day of dosing
Combined ^b elevations of AST or ALT, and Total Bilirubin	
For patients with normal baseline ALT and AST and total bilirubin value: AST or ALT >3.0xULN combined with total bilirubin >2.0 x ULN without evidence of cholestasis ^c OR For patients with elevated baseline AST or ALT or total bilirubin value: [AST or ALT>2x baseline AND > 3.0 xULN] OR [AST or ALT > 8.0 xULN] combined with [total bilirubin >2x baseline AND >2.0 xULN]	Discontinue study treatment permanently. Repeat LFTs as soon as possible, preferably within 48 hours from awareness of the abnormal results, then with weekly monitoring of LFTs*, or more frequently if clinically indicated, until AST, ALT, or bilirubin have resolved to baseline or stabilization over 4 weeks. Refer to Section 6.2.6 for additional follow-up evaluations as applicable.
Reactivation of HBV or HCV	Please refer to Table 6-7 , Table 6-8 .
*LFTs include albumin, ALT, AST, GGT, total bilirubin (fractionated [direct and indirect] if total bilirubin > 2.0 x ULN) and ALP (fractionated [quantification of isoforms], if alkaline phosphatase > 2.0 x ULN). Refer to Section 6.2.6 for additional follow-up evaluations.	
Pancreatic^d	
Asymptomatic grade 1 or 2 amylase or lipase increased (>ULN – 2.0 x ULN)	Maintain dose level
Asymptomatic grade 3 or greater amylase or lipase increased (> 2.0 - > 5.0 x ULN)	Omit/delay dose until resolved to ≤ G2, then: If resolved in ≤ 7 days, maintain dose level If resolved in > 7 days, then ↓ 1 dose level
Asymptomatic grade 4 (> 5.0 x ULN)	Discontinue does and patient form study treatment
Symptomatic elevations of any grade	Discontinue does and patient form study treatment

Recommended dose modifications of INC280	
Worst toxicity CTCAE v4.03 grade	Recommended dose modifications any time during a cycle of therapy, including intended day of dosing
Neurologic	
Any Neurological Toxicity Grade 2	Discontinue study treatment. Neurological assessments must be repeated at least twice a week until resolution to < CTCAE grade 1. Unscheduled MRI and gadolinium enhanced T1 imaging may also be conducted to evaluate patients for intramyelinic edema like lesions, brain metastases and other unanticipated CNS occurrences. An EEG may be performed to monitor for physiological changes in brain activity.
Cardiac	
Cardiac general Grade 1 or 2 Grade 3 Grade 4	Maintain dose level Discontinue dose until resolved to ≤ grade 1, then ↓ 1 dose level Discontinue dose and patient from study treatment
ILD / pneumonitis	
Monitor patients for pulmonary symptoms indicative of ILD/pneumonitis. In addition, withhold INC280 for acute onset of new or progressive unexplained pulmonary symptoms, such as dyspnea, cough and fever and during diagnostic workup for ILD/pneumonitis to exclude alternative causes such as, but not limited to infections, lymphangitic carcinomatosis, cardiogenic edema, or pulmonary hemorrhage.	
Grade 1	Interrupt INC280 during diagnostic workup for ILD/Pneumonitis. Exclude infections and other etiologies. In presence of diagnosis of ILD/Pneumonitis after diagnostic workup, it is mandatory to permanently discontinue INC280. Only in the absence of a diagnosis of ILD/Pneumonitis, INC280 may be restarted at the same dose. If it recurs after resumption of study drug, permanently discontinue INC280.

Recommended dose modifications of INC280	
Worst toxicity CTCAE v4.03 grade	Recommended dose modifications any time during a cycle of therapy, including intended day of dosing
Grade 2	
Mandatory: Interrupt INC280 dose during diagnostic workup for ILD/pneumonitis until improvement to \leq Grade 1. Exclude infections and other etiologies.
 
In presence of diagnosis of ILD/Pneumonitis after diagnostic workup, it is mandatory to permanently discontinue INC280.
 
Only in the absence of a diagnosis of ILD/Pneumonitis, INC280 may be restarted following these guidelines:
 
 · If resolves to \leq Grade 1 in \leq 7 days reduce study drug by 1 dose level · If fails to resolve to \leq Grade 1 within 7 days or recur after resumption of study drug at decreased dose, permanently discontinue INC280.
Grade 3 and Grade 4	Mandatory: Permanently discontinue INC280. Treat with IV steroids as clinically indicated. Oxygen therapy as indicated
Other adverse events	
Grade 1 or 2	Maintain dose level
Grade 3	Discontinue dose until resolved to \leq grade 1, then \downarrow 1 dose level
Grade 4	Discontinue study treatment

^a If total bilirubin $> 3.0 \times$ ULN is due to the indirect (non-conjugated) component only, and hemolysis as the etiology has been ruled out as per institutional guidelines (e.g. review of peripheral blood smear and haptoglobin determination), then \downarrow 1 dose level of INC280, and continue treatment at the discretion of the Investigator
 
^b "Combined" defined as: total bilirubin increase to the defined threshold concurrently with ALT/AST increase to the defined threshold
 
If combined elevations of AST or ALT and total bilirubin do not meet the defined thresholds, please follow the instructions for isolated elevation of total bilirubin and isolated elevation of AST/ALT, and take a conservative action based on the degree of the elevations (e.g. discontinue treatment at the situation when omit dose is needed for one parameter and discontinue treatment is required for another parameter). After all elevations resolve to the defined thresholds that allow treatment re-initiation, re-start the treatment either at the same dose or at one dose lower if meeting a criterion for dose reduction
 
^c "Cholestasis" defined as: ALP elevation ($>2 \times$ULN and R value <2) in patients without bone metastasis, or elevation of ALP liver fraction in patients with bone metastasis
 
Note : The R value is calculated by dividing the ALT by the ALP, using multiples of the ULN for both values. It denotes whether the relative pattern of ALT and/or ALP elevation is due to cholestatic (R\leq2), hepatocellular (R\geq5), or mixed (R>2 and <5) liver injury
 
^d A CT scan or other imaging study to assess the pancreas, liver, and gallbladder must be performed within 1 week of the first occurrence of any \geq Grade 3 of amylase or lipase.
	

Table 6-6 Follow-up evaluations for selected toxicities

Toxicity	Follow-up evaluation
Hematology	If febrile neutropenia of any duration occurs, the patient must be followed until resolution. If \geq CTCAE grade 3 hematologic toxicity occurs, the parameter must be repeated at least twice a week until resolution to \leq CTCAE grade 1 and then at least weekly until either initiation of retreatment or until stabilization.
Renal	If serum creatinine \geq CTCAE grade 2 has been demonstrated, this parameter must be repeated at least twice a week until resolution to \leq CTCAE grade 1 or baseline, and then at least weekly until either initiation of re-treatment or until stabilization. Patients will be instructed to increase hydration until resolution to \leq CTCAE grade 1 or baseline.
Hepatic	In case of isolated elevations in total bilirubin, AST or ALT, additional follow-up evaluations are recommended as outlined in Table 6-9 .
Pancreatic	If serum amylase or serum lipase \geq CTCAE grade 3, follow until resolution to grade 2 or less.
Neurologic	If any neurological abnormality or toxicity \geq grade 2 has been demonstrated, neurological assessments must be repeated at least twice a week until resolution to \leq CTCAE grade 1. Unscheduled MRI and gadolinium enhanced T1 imaging may also be conducted to evaluate patients for intramyelinic edema like lesions, brain metastases and other unanticipated CNS occurrences. An EEG may also be performed to monitor for physiological changes in brain activity.
Cardiac	Monitor toxicity until resolution to grade 1 or baseline. If applicable, monitor electrocardiograms (ECGs) twice weekly until normalization or stabilization.
Non-laboratory	Patients who experience non-laboratory DLTs must be evaluated at least once a week following demonstration of the toxicity until resolution of the toxicity to allow for re-treatment, until stabilization of the toxicity, or until study completion.

Table 6-7 Guidelines for the management of hepatitis B reactivation

HBV-DNA OR HBsAg in baseline result	Definition of reactivation	Treatment
+	Increase of 1 log in HBV-DNA relative to baseline HBV- DNA value	
Provide antivirus treatment *
 
AND
 
Interrupt study drug administration until: ≤ baseline HBV-DNA levels
 
If resolution occurs within ≤ 21 days, study drug should be restarted at one dose lower, if available (see Table 6-2 and Table 6-3 for dose level available).
 
If the patient is already receiving the lowest dose of study drug according to the protocol, the patient should restart at the same dose after resolution.
 
If resolution occurs >21 days, patients should discontinue study drug but continue antiviral therapies at least 4 weeks after last dose of study drug.

- / HBsAb (+) (with no prior history of vaccination against HBV or HBcAb(+)	New appearance of measurable HBV-DNA	
Provide antivirus treatment*
 
AND
 
Interrupt study drug administration until resolution: ≤ undetectable (negative) HBV-DNA levels
 
If resolution occurs within ≤ 21 days, study drug should be restarted at one dose lower, if available (see Table 6-2 and Table 6-3 for dose level available).
 
If the patient is already receiving the lowest dose of study drug according to the protocol, the patient should restart at the same dose after resolution.
 
If resolution occurs >21 days, patients should discontinue study drug but continue antiviral therapies at least 4 weeks after last dose of study drug.

*Antivirus treatment will be provided under discretion of investigator according to local clinical practice.

All reactivations of HBV are to be recorded as grade 3 (CTCAE version 4.03 Infections and infestations/Hepatitis viral), unless considered life threatening by the investigator, in which case they should be recorded as grade 4. Date of viral reactivation is the date on which the rise or reappearance of HBV-DNA criteria was recorded.

Table 6-8 Guidelines for the management of hepatitis C reactivation

HCV Reactivation*	
For patients with baseline results :	Discontinue INC280
Detectable HCV – RNA	
Reactivation is defined as :	
ALT elevation to > 5x ULN	
Increase of 1 log in HCV-RNA relative to baseline HCV-RNA value	
For patients with baseline results :	Discontinue INC280
Knowledge of past hepatitis C infection with no detectable HCV – RNA	
Reactivation is defined as :	
New appearance of detectable HCV – RNA	

* All reactivations of HCV are to be recorded as grade 3 (CTCAE Version 4.03 - Infections and infestations/Hepatitis viral), unless considered life threatening by the investigator, in which case they should be recorded as grade 4. Date of viral reactivation is the date on which the rise or reappearance of HCV-RNA (and ALT) criteria was recorded.

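### In Table 6-5, fever with ANC < 0.5 × 10⁹/L that resolves in ≤ 7 days meets two rows with opposite actions: discontinue the patient, or resume one dose level lower

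*Protocol*

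**What the plan says.** Two adjacent hematology rows of Table 6-5 (protocol Section 6.2.5) apply.

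- **ANC decreased.** Grade 4 is ANC < 0.5 × 10⁹/L. The action is "Discontinue dose and patient from study treatment", with no condition on fever or on time to recovery.
- **Febrile neutropenia.** The criterion opens "Febrile neutropenia ANC < 1.0 x 10" (the exponent and unit follow, so 1.0 × 10⁹/L) and adds a temperature threshold. It has no lower ANC bound and no CTCAE grade. Dosing is held until resolution. Then: "If resolved in ≤ 7 days, then resume treatment at ↓ 1 dose level". For slower recovery: "If resolved in > 7 days, then discontinue dose and patient from study treatment".

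Three other texts bear on which row governs.

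- Section 6.2.5 gives a general rule: "All dose modifications should be based on the worst preceding toxicity (CTCAE version 4.03".
- The left column of Table 6-5 is headed "Worst toxicity CTCAE v4.03 grade".
- Footnote b to the table tells sites to "take a conservative action based on the degree of the elevations", but only for combined transaminase and bilirubin elevations.

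**The concern.** A patient with ANC < 0.5 × 10⁹/L necessarily has ANC < 1.0 × 10⁹/L. If that patient also has fever, both rows apply. When the episode resolves within 7 days, one row ends treatment and the other restarts it at a lower dose.

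The outcome also runs against the clinical ordering. A patient with ANC 0.4 × 10⁹/L and no fever must stop. The same count with fever, a worse presentation, can be read as resumable.

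What is at stake is re-exposure after a neutrophil count at which the neighbouring row requires permanent discontinuation, and different handling of the same patient at different sites.

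**Working it through.** There is no planned figure to reproduce. The check compares the two criteria, the actions attached to them, and any rule that might rank them.

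**Step 1. Overlap of criteria.** The febrile row is ANC < 1.0 with fever. The grade 4 row is ANC < 0.5 (both × 10⁹/L). The intersection is ANC < 0.5 with fever.

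**Step 2. Actions for a febrile patient.**

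| ANC (× 10⁹/L) | Resolution | ANC row | Febrile row | Comparison |
|---|---|---|---|---|
| < 0.5 | ≤ 7 days | discontinue patient | resume, one level lower | conflict; febrile row more lenient |
| < 0.5 | > 7 days | discontinue patient | discontinue patient | agree |
| 0.5 to < 1.0 | ≤ 7 days | same dose | one level lower | febrile row stricter |
| 0.5 to < 1.0 | > 7 days | one level lower | discontinue patient | febrile row stricter |

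The lower two lines serve only to show the direction of the table's logic. The two rows use different recovery endpoints there (grade 1 or baseline in the ANC row, plain resolution in the febrile row), so no finding rests on them. Only in the first line does fever make the printed action milder.

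**Step 3. Is there a rule that ranks the rows?**

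- The worst-toxicity rule points to grade 4, and Section 8.1.1 makes grade 4 the highest grade used in the study. But the febrile row has no grade, so the table does not place it above or below grade 4 ANC.
- Grade 4 does not always mean stop in this table. Grade 4 thrombocytopenia resumes one level lower after recovery. So does a first grade 4 creatinine elevation; only a recurrent one ends treatment. A site cannot infer a blanket grade 4 stop.
- Footnote b is limited to hepatic tests.
- Table 6-6 requires febrile neutropenia to be followed to resolution and counts to be repeated. It does not say whether a patient in this cell may restart.

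**Step 4. Where the conflict has a consequence.** It needs a lower dose level (Tables 6-3 and 6-4).

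- Tablets: 400 to 300 mg bid (300/400 = 0.75, 25% below the starting dose) or 300 to 200 mg bid (200/400 = 0.50, 50% below).
- Capsules: 600 to 450 mg bid in the expansion part, or 300 to 200 mg bid in the dose-determining part.
- At 200 mg bid tablets no level remains. The tablet cap agrees: "a maximum of 2 dose level modifications is allowed after which the patient must be discontinued from treatment".

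**Step 5. Effect on the analyses.** Table 6-2 counts both febrile neutropenia and any grade 4 hematologic toxicity as qualifying AEs, so a related event in this cell counts in the dose decision whichever row the site follows. TTP is defined by progression or cancer death, and Section 7.1.5 continues tumor assessments after discontinuation for toxicity. The sample size does not depend on either row.

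**The case against.** The strongest reply is that the protocol already settles the matter. The worst-toxicity rule covers all dose modifications and need not name each row. ANC < 0.5 × 10⁹/L is expressly grade 4, with an unconditional action. A patient who meets two rows should satisfy both, and permission to restart in one does not waive a permanent stop in the other. In addition, Section 6.2.5 requires any modification outside the tables to be discussed with the sponsor.

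Much of this stands. A careful reader would probably stop treatment, and that is why the point is minor. It does not close the gap. The ranking has to be inferred for an ungraded row, in a table where some grade 4 events do allow a restart. The duty to consult applies to departures from the tables, and a site that restarts under the febrile row can say it followed them.

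The second reply is that the practical reach is very small. Bone marrow is not among the target organs in the toxicology summary (Section 1.2.1.1.3), patients with ANC < 1.5 × 10⁹/L are excluded at entry (Section 5.3), and Amendment 6 is dated more than five years after enrollment closed. This also stands. It limits the size of the point, not its correctness.

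A reader might infer something stronger: that the protocol directs re-exposure after grade 4 neutropenia, or has no rule on the question. The documents do not support that. The general rule and the column header both favour discontinuation. The defect is that a printed row permits the opposite and nothing expressly overrides it.

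**Conclusion.** The inconsistency is real and narrow. One combination (ANC < 0.5 × 10⁹/L, fever, resolution in ≤ 7 days) receives two incompatible instructions, and the rule that favours stopping does not expressly rank the febrile row. It is a minor safety-rule inconsistency, worth correcting but not urgent.

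Its reach is limited to patients still on treatment who have a lower dose level available. The documents give no incidence of febrile neutropenia, so no expected number of patients can be stated.

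A reader might also infer that the efficacy result or the choice of expansion dose is in doubt. Neither is: the sample size, the TTP analysis and the qualifying-AE count do not depend on which row a site follows.

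The conclusion rests on reading the grade 4 ANC action as permanent. The wording supports this, because it removes the patient as well as the dose, whereas rows that intend a hold state a recovery condition.

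**What to change.** Keep the febrile neutropenia criterion as it is and add to its ≤ 7 days action: *if ANC was < 0.5 × 10⁹/L (grade 4), discontinue the patient regardless of fever or time to resolution*. This agrees with the grade 4 ANC row and with the worst-toxicity rule.

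Narrowing the febrile row to ANC 0.5 to < 1.0 × 10⁹/L looks equivalent but is not advisable. Table 6-2 defines febrile neutropenia with no lower bound, so the protocol would then hold two definitions of the same event.

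The change is one line of text, with nothing to alter in data collection, the SAP or the analysis. The cost is procedural. Section 12.1 allows changes only through a written amendment approved by the sponsor, the ethics bodies and, where required, health authorities, so a clarification letter is not an available route. Given the small reach, the line can be carried in the next amendment.
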